This is a pilot (Phase II) randomized clinical trial with randomization in a 1:1 ratio. The control group will receive a brief consultation (10-15 minutes via phone) about free or low-cost resources that may help them address unmet social support needs. Additionally, a written directory of a range of social support resources will be delivered via mail. The treatment group will receive the aforesaid intervention plus brief advice to quit smoking (10-15 minutes via phone). Additionally, a written summary of the benefits of smoking cessation, evidence-based approaches to quit, and the basics of NRT in addition to a free, 2-week supply of nicotine patches and lozenges will be delivered via mail. As a pilot, this study focuses on the outcomes of feasibility (i.e., accrual and retention) and acceptability (e.g., participants' perceptions of appropriateness and effectiveness) as opposed to efficacy (though this is also important). Despite the use of an intervention, participants in this study are not "treatment seeking" smokers and the study will not be advertised as an "intervention" or "treatment" for smokers who want to quit. This is because the goal is to encourage the occurrence of quit attempts among smokers who may or may not be interested in smoking cessation in the near future as opposed to promotion of sustained abstinence among smokers who express readiness to quit. The emphasis on smoking cessation induction (that is, the inducement or promotion of a quit attempt) is an important aspect of the study design and is appropriate for smokers across the continuum of motivation to quit. Given the focus on "all comers" with respect to motivation to quit, the behavioral target of quit attempts instead of prolonged abstinence, and a minimal intervention (specifically, a 2-week supply of NRT), the period of follow-up is relatively brief (Day 0 to Day 60, or 2 months). All of the intervention components will be delivered remotely via mail or phone in order to test this intervention in the "real world" where it would be difficult for cancer survivors to travel far for smoking cessation treatment. Finally, it is important to note that biochemical verification of self-reported quit attempts will not occur (see "Alternative Methods" section of the grant for more the rationale). The anticipated start and end of enrollment is 10/01/17 and 07/31/19, respectively. The goal is to enroll 80 cervical and head/neck cancer survivors who at the time of enrollment are within 5 years from the date of cancer diagnosis. In the absence of any preliminary data, it is unknown how the final sample will be split in terms of cervical versus head/neck cancer survivors. The eligibility criteria (see Study Population) were selected to balance the needs of the study with the desire to increase generalizability of study findings to cancer survivors who are at high risk for persistent smoking (i.e., tobacco-related cancer survivors who were smokers at or near the time of cancer diagnosis; [name] et al., 2015). During the course of study participation, participants' health status may vary as a result of living with cancer and any other chronic disease. Nonetheless, this study is not expected to engender more than minimal risk to participants' physical health, as the anticipated adverse events (AE) are most likely to be mild or moderate in severity and short-term in duration (see "Potential Risks").

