provided can be found in the attachment to this section. The final product was already submitted to the IRB and should be on file.) Participants will be called on Day 14 to see if they received the shipment (if not a second shipment can be mailed), to answer any questions, and to encourage use of the informational resources provided as part of this study; this check-in should not last more than 3-5 minutes. After the Day 0 survey, whether it's done via phone or mail, participants in the SS+NRT group will receive the same consultation about free or low-cost resources related to their two most pressing unmet social support needs. In this same call, participants will receive brief advice related to smoking cessation (10-15 minutes). Consistent with the brief advice model described in the latest Clinical Practice Guideline for Treating Tobacco Use and Dependence (CPG-TTUD; Fiore et al., 2008), participants will be informed about the general health benefits of smoking cessation, given an overview of evidence-based approaches to smoking cessation (e.g., stimulus control, medication use, support seeking), and provided with a summary of the mechanism of action and potential benefits/risks of NRT specifically. They will be encouraged to try NRT in the context of a "practice" quit attempt, even if the abstinence they achieve only lasts a few hours. There will not be any pressure to achieve long-term success during the course of study participation, but participants will be told that multiple "practice" quit attempts could result in 1) learning which approaches and coping strategies do vs. do not work for them and 2) increasing their motivation/confidence in their ability to quit for good. It should also be noted that participants will be assured there is no requirement to quit, reduce smoking, or even try NRT as part of this study. The goal of this study is to encourage a "hassle-free" quit attempt. After the consultation, and in the same mailing as the social support resource directory, a free 2-week supply of nicotine patches (14mg; NicoDerm CQ - GlaxoSmithKline) and nicotine lozenge (2 or 4mg; Nicorette - GlaxoSmithKline) will be supplied; participants will be forewarned about the NRT shipment via the US Postal Service metered mail, and given the opportunity to opt out if they like. As for the amount of NRT, each participant who doesn't opt out of the shipment will be mailed one box of 14 nicotine patches (1 patch per day) and one box of 72 nicotine lozenges (2mg or 4mg supply based on time to first cigarette as per the package label, with 1 lozenge per 1-2 hours when awake) in their original packaging. A summary of the information discussed on the phone will be provided. Participants will be called on Day 14 to see if they received the shipment (if not a second shipment can be mailed), to answer any questions, and to encourage use of the informational and medication resources provided as part of this study; again, this check-in should not last more than 3-5 minutes. Participants in both groups will be asked to complete a Day 30 and 60 survey (see Data Collection attachment). Finally, on or shortly after Day 74, all participants will receive a final letter that briefly outlines the importance and benefits of smoking cessation for cancer survivors and provides up-to-date contact information and the latest flyer for the KY Quitline (see attachment in this section). It should be noted that women of childbearing potential will be asked to take a pregnancy exam before consenting to take part in this study because pregnancy is an exclusionary criterion; this is something they will need to do on their own. If participants of childbearing age are assigned to the SS+NRT group, they will be also asked to engage in an effective method of birth control (e.g., abstinence from sex, oral contraceptive, intrauterine contraceptive device) during study participation. Finally, if a woman becomes pregnant during this study, they will be asked to immediately inform the PI who will then have [name], the Medical Supervisor for this study, contact them and advise them on stopping NRT, if appropriate. No information will be entered into participants' EHR as part of this study.

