Participants will receive \$25 for each survey, which means they can earn up to \$75 total. Payment for the baseline and follow-up surveys are the same despite differences in the length of the surveys in order to incentivize participants against dropout. This is a common approach for survey research, especially in the case of clinical trials, and is not considered problematic in any way. Participants will be paid for whatever survey(s) they complete, even if they formally withdraw from the study or do not complete the study in its entirety. Payment will be initiated within three weeks of completing the assessment in the form of a check that is disbursed by the UK Department of Psychology's Integrated Business Unit.

Costs to Subjects: Describe any costs for care associated with research (including a breakdown of standard of care procedures versus research procedures), costs of test drugs or devices, and research procedure costs that are the subject's responsibility as a consequence of participating in the research. Describe any offer for reimbursement of costs by the sponsor for research related injury care.

The directory of social support resources, and if applicable, the 2-week supply of NRT, will be provided to participants at no cost. The only known cost for participants is the time they spend completing the surveys and speaking to the study coordinator. However, if participants seek medical or other care for any research-related AEs, they will be responsible for these costs.

Data and Safety Monitoring: The IRB requires review and approval of data and safety monitoring plans for greater than minimal risk research, clinical research, or NIH-funded/FDA-regulated clinical investigations.

If you are conducting greater than minimal risk research, clinical research, or your clinical investigation is NIH-funded/FDA-regulated, describe your Data and Safety Monitoring Plan (DSMP). [Click here for additional guidance on developing a Data and Safety Monitoring Plan.](#)

If this is a *non-sponsored investigator-initiated* protocol considered greater than minimal risk research, clinical research, or your clinical investigation is FDA-regulated, *and* if you are planning on using a Data and Safety Monitoring Board (DSMB) as part of your DSMP, [click here for additional guidance](#) for information to include with your IRB application.

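### Do 72 lozenges fall short of the two-week supply the protocol describes, and does the plan need to change because of it?

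*Combined protocol and SAP*

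**What the plan says.** The two-week label appears in four places in the protocol. Two of them name both products:

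- Study Design, on what the treatment group receives: "a free, 2-week supply of nicotine patches and lozenges will be delivered via mail".
- Research Procedures: "a free 2-week supply of nicotine patches (14mg; NicoDerm CQ - GlaxoSmithKline) and nicotine lozenge".

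Two refer to nicotine replacement therapy (NRT) in general:

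- Study Design, on why follow-up is short: "a minimal intervention (specifically, a 2-week supply of NRT".
- Costs to Subjects: "the 2-week supply of NRT, will be provided to participants at no cost".

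Research Procedures also sets out the parcel: "one box of 14 nicotine patches (1 patch per day) and one box of 72 nicotine lozenges". A parenthesis then says that lozenge strength follows time to first cigarette as on the package label, and adds "with 1 lozenge per 1-2 hours when awake". Participants are called on Day 14 "to see if they received the shipment (if not a second shipment can be mailed"; this replaces a lost parcel and is not a refill. They are also told that "there is no requirement to quit, reduce smoking, or even try NRT as part of this study".

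**The concern.** One sentence puts a duration on both products, and the count and rate that follow do not give that duration for the lozenges. The label helps to describe the experimental arm, and Study Design names the intervention by it. A reader who sees only the Study Design summary could suppose that two weeks of lozenges at the stated rate were mailed, and so credit the arm with more product than it received. Someone repeating the pilot or pooling it with other sampling trials could carry that error forward. Nothing elsewhere removes the mismatch: no section limits the label to patches, says the lozenges are for partial or as-needed use, or provides a refill.

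**Working it through.** **Inputs**

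- Labelled duration: 2 weeks = 14 days (Study Design; Research Procedures).
- Patches: 14, one per day (Research Procedures).
- Lozenges: 72, one per 1 to 2 waking hours (Research Procedures).
- Waking hours per day: not in the documents. Assumed 16, with a range of 12 to 18.

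**Formulas**

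Lozenges per day = waking hours / interval between lozenges. Days of supply = units mailed / units per day.

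**Patches**

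14 / 1 = 14 days. The label is reproduced.

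**Lozenges**

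| Waking hours | Lozenges per day (every 2 h to hourly) | Days 72 lozenges last | Share of 14 days | Lozenges used in 14 days at the stated rate |
|---|---|---|---|---|
| 12 | 6 to 12 | 72/12 = 6 to 72/6 = 12 | 43% to 86% | 84 to 168 |
| 16 | 8 to 16 | 72/16 = 4.5 to 72/8 = 9 | 32% to 64% | 112 to 224 |
| 18 | 9 to 18 | 72/18 = 4 to 72/9 = 8 | 29% to 57% | 126 to 252 |

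The last column shows the size of the gap and is not a proposed quantity.

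Working backwards, 72 / 14 = 5.14 lozenges a day. That is one every 16 / 5.14 = 3.1 hours at 16 waking hours (2.3 hours at 12, 3.5 hours at 18), always outside the stated interval. At the slowest stated rate, 72 lozenges reach 14 days only if the waking day is no longer than 5.14 × 2 = 10.3 hours. So the waking-hours assumption does not decide the result: no value from 12 to 18 hours gives 14 days.

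**The general wording**

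The two phrases that speak only of NRT are not shown to be wrong, because 14 patches at one a day supply NRT for 14 days. Only the two phrases naming both products conflict with the lozenge figures.

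**What depends on the number of lozenge days**

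- Accrual (SAP, Outcome Measures, item 1) is the number enrolled over the number contacted. Supply does not enter.
- Retention (item 2) is end-of-study assessments over the number enrolled. Supply does not enter.
- Acceptability (item 3) is a mean total score compared by t-test. It reflects the parcel participants actually received, whatever the protocol calls it.
- The hypotheses under Objectives concern motivation, confidence, any use of NRT, a 24-hour quit attempt and 7-day abstinence. None is defined by days of supply.
- The target of 80 participants is not derived from the supply, and neither document gives a power calculation or threshold that uses it.
- Follow-up runs to Day 60, well beyond the supply whether the lozenges last 4 days or 14.

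**The case for a change.** The strongest case for a change is that the contradiction is genuine, sits within a single section, and would cost a few phrases to remove. Background describes sampling kits as lasting two to six weeks and says that combining a patch with a short-acting product works better than one product alone. At the stated rate and 16 waking hours, the combination would run out with 14 − 9 = 5 to 14 − 4.5 = 9.5 days of patch-only supply left. On that view the label overstates what the arm offers, and puts the lozenges at the lower edge of a range that they fall below.

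The arithmetic stands, and so does the remark that no section declares the lozenges to be as-needed. The conclusion drawn from it is weaker, for four reasons:

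- The rate appears once, in a parenthesis, directly after a reference to the package label. It can be read as repeating label directions and not as a schedule for emptying the box. The package insert, the lozenge study drug form and the written summary mailed to participants are not shown, so the documents cannot settle the reading.
- Using the box at the full rate is not a planned course here. The protocol encourages a trial quit attempt even of a few hours and leaves use entirely to the participant, so a box may well last two weeks or more in practice.
- A reader repeating or pooling the trial need not infer a lozenge count from the label. Research Procedures gives it. Under Data and Safety Monitoring, the principal investigator also records every shipment by product, quantity, dose and date, and the drug service keeps accountability logs.
- The discrepancy runs towards less product than the label implies, so it does not contradict the short-duration safeguard in Safety Precautions.

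Describing the arm by its contents in publications would be good practice, but that is a reporting preference and not an error in the plan.

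**Conclusion.** This is a clerical slip in a descriptive label. Two phrases, one in Study Design and one in Research Procedures, call the lozenges a two-week supply. At the quantity and rate given in Research Procedures, the box lasts 4.5 to 9 days at 16 waking hours and 4 to 12 days across 12 to 18 hours. That rests on an assumed waking day and on reading the stated rate as the rate of use. The duration wording and the lozenge figures should be reconciled as a matter of text; the choice is the sponsor's, and none is suggested here.

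No change to the plan follows. With or without the rewording, the same 14 patches and 72 lozenges are mailed, the same shipment records are kept, and the same accrual, retention and acceptability results are obtained. No sample size, test, threshold or hypothesis moves.

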The overall risks to participants are low in terms of both their likelihood and seriousness. The physical risks associated with use of nicotine patch and/or nicotine lozenge in this study are expected to be rare and mild. In prior studies of NRT (many of which have much longer sampling periods), adverse events were documented to occur in the majority of participants (~70%), but dropout due to AEs was low (~7%) and the report of serious AEs was even lower (~2%) (e.g., Carpenter et al., 2011; Jardin et al., 2014). The most common AEs for the NRT under study here are skin irritation (patch), headache (patch), insomnia (patch), mouth and throat soreness (lozenge), hiccups (lozenge), and nausea (patch and lozenge) (Hughes et al., 2004; Mills et al., 2010; Piper et al., 2011). It should be appreciated that concurrent use of cigarettes and NRT, which rarely occurs (Shiffman, Hughes, DiMarino, & Sweeney, 2003), is now considered to be safe (Fagerstrom & Hughes, 2002) despite the risk for nicotine "overdose" or "intoxication" as characterized by nausea, vomiting, dizziness, diarrhea, weakness, and rapid heartbeat. Therefore, the FDA now suggests that it is unnecessary to quit smoking before starting NRT and it is unnecessary to stop NRT if lapse or relapse to smoking occurs. The psychological risks are those associated with being asked questions about the following: 1) demographics, including access to health care, 2) cancer survivorship, 3) quality of life, 4) tobacco use and cessation, and 5) social environment/relationships. Although completion of the surveys might result in mild emotional discomfort, based on the PI's experience, the likelihood of psychological risk is low and the severity of this risk is mild. Furthermore, participants always have the option of not completing a survey or skipping an item. It should be noted that the extant data on NRT sampling (as opposed to provision or recommendation of a full, standard dose of NRT) does not suggest that it undermines smoking cessation, thus reductions in motivation, confidence, and behavior change are considered to be very low in likelihood and severity. There are confidentiality risks. The health-related and other private information obtained from KCR, EHR, and participants is considered sensitive in nature, and a breach of confidentiality for these data could pose a mild to moderate risk to participants. Since especially sensitive information regarding sexual orientation, criminal history, or a history of treatment for substance abuse/dependence (other than treatment for nicotine dependence) will not be collected for this study, the consequence of an individual's survey responses being revealed is thought to be mild. However, to minimize any adverse consequences of a breach of confidentiality for these data, solely participants' unique identification number will identify all survey data. The financial risks are the costs associated with regular use and maintenance of a landline or cellular phone. These risks are likely to be of little consequence, given that no one is required to modify their pre-existing phone access as part of study procedures. Finally, it should be noted that mailing NRT is a very well-accepted method to disseminate NRT (Carpenter et al., 2011 Archives of Internal Medicine; Cunningham et al., 2016 JAMA Internal Medicine; Kushner et al., 2017 Addictive Behaviors; Jardin et al., 2014 Nicotine and Tobacco Research; Solomon, Scharoun, Flynn, Secker-Walker, & Sepinwall, 2000 Preventive Medicine; Zawertailo et al., 2012 Tobacco Control). This is standard practice for state Quitlines, and like the Quitlines, NRT will be mailed to participants sans tracking or signature confirmation, both of which add unnecessary cost and burden to the procedures and participants alike. The approach proposed here is considered acceptable for several reasons, including largely NRT's over-the-counter status, relatively benign adverse event profile, and low abuse liability (West et al., 2000; Psychopharmacology) coupled with the fact that the treatment group in this study actually gains access to an evidence-based treatment for smoking cessation as part of study participation.

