The primary protection against the physical risks associated with both nicotine patch and nicotine lozenge (both over-the-counter medications) is that it will only be provided for a short duration and smokers with FDA contraindications will not be enrolled in this study. Second, the Data and Safety Monitoring Plan (DSMP) includes AE monitoring, and the PI, RAs, and Medical Supervisor ([name]) will work closely together to make sure that participants' AEs are handled in a timely and responsible manner. Third, females of childbearing potential will be asked to use effective contraception to guard against pregnancy during the course of the study (this is on top of exclusion criteria related to pregnancy/breastfeeding). Fourth, participants will be encouraged to contact the PI and stop the use of the nicotine patch and consult with their physician or advanced practice registered nurse as instructed on the package insert. Finally, participants who report a serious AE will be withdrawn from the study. Several steps will be taken to minimize psychological risks. First, participants will be alerted to the possibility of mild emotional discomfort prior to their enrollment in the study, as the consent form will provide information about the nature of the surveys. Second, participants will be assured via the consent form and verbal assurances from the PI and RAs that their data are confidential. Third, participants will be allowed to skip any question or withdraw from the study at any time. Finally, participants who experience emotional discomfort as a result of this study will be: 1) allowed to withdraw from the study without penalty and 2) provided with contact information for mental health professionals near their place of residence. Note that as a licensed clinical psychologist in Kentucky, the PI has access to a list of licensed psychologists and related mental health professionals who practice throughout the state, and can provide said information to anyone who requests it. To address confidentiality risks, well-established guidelines for security best practices will be followed, with particular attention to guidelines for data collected electronically. Although not specific to this study, both KCR and UK HealthCare have established safety precautions: 1) KCR has an established means of encrypted electronic file transfer that involves unique username and password authentication, and will only release participant data through that avenue and 2) UK HealthCare Enterprise has an established means of training everyone prior to granting them access to one or more of their EHR systems, and once access is given, an audit trail is created via the requirement of unique username and password authentication prior to each log-in. The safety precautions specific to this study are as follows: First, the responses of any one participant will never be reported apart from those of other participants. Second, all participants will be assigned a unique identification number. Only participants' unique identification number will identify their survey data. Within a month of receiving participants' health information from KCR, these data will be coded such that only participants' unique identification number is associated with their health information (e.g., if names are used to identify cases in the file given to me by the registry, then the names will be removed and replaced with participants' unique identification number). In this way, only participants' unique identification number will identify their sensitive health information and survey data. Third, the electronic document that links participants' unique identification number with their private individually identifiable information (i.e., name, address, phone number) will be strictly protected (only the PI and RAs will have access), password protected, and stored on a secure server maintained by the UK College of Arts & Sciences. Fourth, the electronic document that contains a list of patients to be screened will be strictly protected (only the PI and RAs will have access), password protected, and stored on a secure server maintained by the UK College of Arts & Sciences. Fifth, this study will use UK computers that will: 1) be protected from access by outside parties through the use of a firewall, 2) be password protected, 3) have regular backups performed, and 4) have operating system patches and antivirus software kept up-to-date. These computers will be physically housed on the 2nd and 3rd floor of the UK Combs Cancer Research Building and the basement and 2nd floor of UK Kastle Hall, as the PI's office and lab space is spread across these two buildings. Sixth, access to electronic study files will be restricted to the PI and select RAs, and all individuals who are granted access will need to pass through username and password authentication as these files will be stored on the College of Arts & Sciences secure server. Similarly, access to paper study files will be restricted to key study personnel, as these files will be kept in lockable filing cabinets that are stored on the basement floor of the Kastle Hall behind locked doors. Seventh, the surveys will be administered with the use of Research Electronic Data Capture (REDCap) whenever they are done by phone, and whenever they are done by paper, participants' responses will then be entered into REDCap. REDCap is designed to provide a secure, reliable, and valid means of electronic data capture as it will: 1) operate behind a firewall on a secure UK server, 2) minimize data entry errors via automatic data validation, 3) provide a "real time" searchable log of input and output, and 4) allow the creation of audit trails. Seventh, any transfer of electronic files between the PI and KCR will be completed using their established means of encrypted file transfer that involves unique username and password authentication. Finally, all study personnel will maintain up-to-date human subjects protection training. It should also be noted that we will not retain beyond the anticipated end of the study (07/31/20) the name or contact information (i.e., phone number and mailing address) for cancer survivors who "opt in" to KCR's releasing this info to the PI, but ultimately do not enroll in the study. Additionally, we will not retain beyond the aforesaid date the list of patients to be screened as part of the clinic-based recruitment. That is, unless someone provides written informed consent to study participation, we will not keep a record of his or her personal information. This personal information will be destroyed according to UK Policy A13-050. Financial Risks: These risks will be explained to potential participants as part of the informed consent process and will be offset by the financial compensation participants will receive.

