health information and participant-provided survey data will be identified only by participants' unique identification number, and the document that links participants' unique identification number with their individually identifiable contact information (i.e., name, address, and phone number) will be strictly protected via entry that requires a 2-step username and password authentication. Other guidelines for security best practices will be followed and are described above (see "Confidentiality"). Quality Assurance. As a recipient of a Career Development Award, the PI has regular meetings with a more senior faculty person who serves as a mentor: [name], Co-Investigator for this study. Additionally, the PI maintains weekly meetings with all RAs to discuss problems with or concerns about data gathered in all studies. As it pertains to data collection, REDCap will assist in quality assurance (see "14. Confidentiality"). Once all data are collected, preliminary data analysis done by the study biostatistician ([name]) will provide a check for quality, the results of which will guide all subsequent data analysis. DSMP Administration and Other Regulatory Issues. This study will be registered on ClinicalTrials.gov prior to the start of enrollment and will be updated as required. Filing for an Investigational New Drug (IND) application with the FDA is not appropriate for this study, as the FDA has stated so several times in the past for studies that very closely align with this one (as per [name], one of the PI's mentors). The PI will be responsible for monitoring all the human subjects aspects of this study. She will be responsible for reporting all adverse events (including whether or not they are related to study participation) to the IRB and funding agency at the appropriate times; a report will be submitted at least once a year, but this could occur more frequently if the circumstances call for immediate disclosure (e.g., in the case of a serious AE). If any significant action is taken by the IRB in response to an AE, procedural changes will be relayed to granting agency. In addition, the PI will report any change to the study's risk/benefit ratio to the IRB as soon as she becomes aware of it and will modify the informed consent procedures to reflect such change. The PI will also ensure that any conflicts of interest will be reported for all presentations and manuscripts that result from this study. Finally, the UK IRB and Markey Cancer Center's Protocol Review Monitoring Committee will provide oversight for this study, and the PI will seek their approval and enforce their regulations at all times.

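### AE monitoring is named as a protection, but the text gives no method or timing for asking about AEs, and the SAP has no AE summary by arm

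*Combined protocol and SAP*

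**What the plan says.** **Design.** Study Design states: "This is a pilot (Phase II) randomized clinical trial with randomization in a 1:1 ratio". It adds: "The goal is to enroll 80 cervical and head/neck cancer survivors". The NRT arm gets the social support intervention plus brief advice, and a "free, 2-week supply of nicotine patches and lozenges will be delivered via mail". Research Procedures lets participants decline the shipment and tells them that they need not try NRT.

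**Expected harm.** Potential Risks says that the physical risks of patch and lozenge in this study are "expected to be rare and mild". Its next sentence reports that in prior NRT studies "adverse events were documented to occur in the majority of participants (~70" percent), with AE dropout of about 7% and serious AEs of about 2%. It notes that many of those studies sampled for much longer. Study Design describes the anticipated AEs as mostly mild or moderate.

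**Monitoring.** Safety Precautions counts as its second protection that "the Data and Safety Monitoring Plan (DSMP) includes AE monitoring". In the Data and Safety Monitoring section, the PI monitors the human-subjects aspects of the study. On AEs the text says: "She will be responsible for reporting all adverse events", to the IRB and the funder, at least yearly.

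**Contacts.** On the mid-study call, Research Procedures says: "Participants will be called on Day 14 to see if they received the shipment". The call also answers questions and encourages use of the materials. Surveys follow on Days 30 and 60. Research Materials, Records and Privacy names two data sources, the cancer registry and the surveys.

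**Analysis.** The SAP lists accrual, retention and acceptability. It has no safety outcome or table.

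**The concern.** Safety Precautions points to the DSMP for AE monitoring, and the DSMP does not say how AEs are found. It gives no question, schedule, form, grading or recall window. A duty to report all AEs presupposes a way of learning about them.

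The one route described is initiated by the participant: Safety Precautions encourages contact with the PI in connection with use of the nicotine patch. Delivery and data collection are remote, so there is no study visit at which staff would notice an event. Participants in the control arm have little reason to report under a prompt that concerns NRT. Study Design also expects health status to vary because of cancer and other chronic disease, so background symptoms will occur in both arms.

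Two things are at stake. First, tolerability bears on whether mailed NRT is feasible and acceptable, which is the focus of the pilot. Second, the protocol withdraws participants who report a serious AE, and that provision works only if events are reported. If ascertainment differs by arm, any AE counts by arm would mix an NRT effect with a reporting effect.

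**Working it through.** The documents derive no AE count, power or capture rate, so there is no planned figure to reproduce. The check has two parts.

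**1. Where could an AE be recorded, as described?**

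| Contact or text | Stated content | AE question described? |
|---|---|---|
| Day 14 call | Receipt, questions, encouragement | No; also not a named data source |
| Day 30 and 60 surveys | Set out in attachments not shown | Cannot be determined |
| Survey topics in Potential Risks | Demographics, survivorship, quality of life, tobacco, social environment | AEs not named, but the list explains psychological risk and is not an item inventory |
| Safety Precautions | Participant contacts the PI; staff handle AEs together | Participant-initiated |
| DSMP | PI monitors and reports | No collection method |
| SAP | Accrual, retention, acceptability | No AE summary |

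**2. What size could this have?**

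Inputs: 80 participants at 1:1, so 80 / 2 = 40 per arm; prior-study rates of about 70% (any AE), 7% (dropout due to AEs) and 2% (serious AE), from Potential Risks.

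Expected number = n × p:
- Any AE: 40 × 0.70 = 28
- Dropout due to AEs: 40 × 0.07 = 2.8
- Serious AE: 40 × 0.02 = 0.8; chance of at least one = 1 − 0.98^40 = 0.554

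These carry prior-study rates over to all 40 participants. No rate is given for a two-week supply. Over an assumed range of 10% to 50%, the expected number is 40 × 0.10 = 4 to 40 × 0.50 = 20.

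Number missed = 28 × (1 − c), where c is the share of participants with an AE who come to the study's notice. The documents give no value for c, so these values are assumed:

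| c | Recorded | Missed |
|---|---|---|
| 10% | 2.8 | 25.2 |
| 25% | 7 | 21 |
| 50% | 14 | 14 |
| 75% | 21 | 7 |

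The result depends almost wholly on c, so the extent of under-capture cannot be stated.

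The effect of unequal capture can be illustrated. Assume a true rate of 30% in both arms (40 × 0.30 = 12 each), with capture of 50% in the NRT arm and 25% in the control arm. The record would show 12 × 0.50 = 6 against 12 × 0.25 = 3, although the arms do not differ.

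**What a descriptive table could show.** For 28 of 40, the exact 95% CI is 53% to 83%. For 0 of 40, the exact upper limit is 1 − 0.025^(1/40) = 8.8%. These intervals are wide but suit a pilot.

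**The case against.** The strongest reply is that the content of the surveys is not visible. The list of measures and the questionnaires are attachments, and tobacco-use items could well cover NRT side effects. This stands: one may say only that the text describes no elicitation, not that none exists. It does not settle the Day 14 call, whose purpose the protocol does describe.

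A second reply is that more oversight exists than a bare reporting duty. The PI, research assistants and Medical Supervisor work together on AEs, the team meets weekly, a cancer-center monitoring committee is named, and the Day 14 call invites questions. This also stands, but each of these acts on events already known, and an open invitation to ask questions is not a standard AE question.

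A third reply is that safety is not an aim of this pilot, the products are sold over the counter and the control arm gets none. That argues against a formal safety test. It does not argue against a descriptive table.

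Four stronger readings are tempting, and the documents do not support them:

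- *Most AEs will go unrecorded.* This needs capture below 50%, and no capture figure is given.
- *About 28 participants will have an AE, and a serious AE is more likely than not (55%).* Both figures treat all 40 as exposed and use rates from studies of which many sampled for much longer. If the serious AE rate were halved (assumed), the chance of at least one would be 1 − 0.99^40 = 33%.
- *The protocol hides a high AE rate behind the word rare.* The figure of about 70% appears in the very next sentence with its qualifier, and it does not contradict mild.
- *The trial collects no AE data.* The unseen questionnaires rule out this conclusion.

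**Conclusion.** The concern holds in a limited form. AE monitoring is listed as a protection, but neither the DSMP nor the described contacts say how or when participants are asked about AEs, and the SAP plans no AE summary. As written, events during NRT use become known mainly through volunteered reports, so capture could be incomplete and could differ by arm.

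The size cannot be computed. The figure of 28 of 40 is an upper-end illustration that assumes the prior-study rate applies to everyone in the NRT arm. The conclusion about the Day 14 call rests on the protocol's description of that call. The conclusion about Days 30 and 60 is conditional on questionnaires that are not shown. The primary feasibility and acceptability results are not invalidated. This is a cheap improvement to safety ascertainment, with a minor inconsistency in how expected harm is worded.

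**What to change.** 1. **Ask.** Add one fixed AE question to the existing Day 14 call, worded identically in both arms. Add it to the Day 30 and Day 60 surveys if they do not already contain one; if they do, cite the items. State the method and timing in the DSMP, and list the Day 14 call as a data source.
2. **Summarize.** Add a descriptive table by arm to the SAP: participants with any AE, with an AE leading to stopping NRT (NRT arm only), and with a serious AE. Give exact 95% CIs, the number asked at each contact, and no formal test.
3. **Reconcile the wording.** Bring "expected to be rare and mild" in Potential Risks into line with the cited rate of about 70% and with the severity described in Study Design.

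The cost is one or two minutes per call, an IRB modification and one table. More mild AEs will be recorded and will need reporting. If follow-up is already complete, the table is still possible, with a plain statement of how AEs were ascertained in each arm.
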